### **7.5.3.3 Current status of Progression Free Survival follow-up**

Time from last tumor assessment to data cut-off in months will be summarized by treatment arm. Subjects who have a PFS event will be considered as current for this analysis. The secondary definition of PFS will be used for this summary.

By-subject listings will also be produced to accompany the subject time from last tumor assessment table for all randomized subjects.

[REDACTED]

[REDACTED]

[REDACTED]

### **7.5.3.6 Subsequent Therapy**

The following information pertaining to subsequent therapies will be summarized for all randomized subjects by treatment arm, as randomized:

Number and percentage of subjects receiving subsequent therapies including:

- Immunotherapy (anti-PD1 agents, anti-PD-L1 agents, anti-CTLA-4 agents and others) by drug name
- Other agents excluding Nivolumab (approved and investigational) by drug name
- Surgery
- Radiotherapy
- Any combination of the above

A subject listing of follow-up therapy will be produced for subjects who had any subsequent therapy for all randomized subjects.

### **7.5.4 Overall Survival**

#### **7.5.4.1 Primary Analysis of Overall Survival**

OS distribution for each treatment arm will be estimated using Kaplan Meier technique and will be displayed graphically in the platinum refractory and platinum eligible subgroups, separately. Median Survival time in each arm along with 95% CI will be constructed based on a log-log transformed CI for the survivor function. The hazard ratio and the 95% confidence interval will be estimated in a stratified Cox proportional hazards model using the randomized arm as a single covariate, stratified by PD-L1 status and HPV p-16 status, in the platinum refractory and platinum eligible subgroups, separately. OS rates at 6, 9, 12, 18, 24, 36, 48 and 60 months with 95% CIs will be estimated using Kaplan-Meier methodology. These analyses will be performed only if the minimum follow-up for OS has been reached corresponding to that endpoint.

The status of subjects who are censored in the OS KM analysis will be tabulated for each randomized treatment group using the following categories:

- On-study (on-treatment, in follow-up)
- Off-study (lost to follow-up, withdrawn consent, never treated)

To examine the assumption of proportional hazards in the Cox regression model, in addition to treatment, a time-dependent variable, in the form of a treatment by time interaction, will be added into the model. A two-sided Wald Chi-square p-value of less than 0.1 may indicate a non-constant hazard ratio.

#### **7.5.4.2 Overall Survival Sensitivity Analyses**

The following OS sensitivity analyses will be performed.

- OS using stratification factors as obtained from the baseline CRF pages and clinical database (instead of IVRS). The hazard ratio associated with treatment will be presented along with the associated two-sided 95% CIs. This analysis will be performed only if the stratification

variable/factor at randomization (as per IVRS) and baseline are not concordant for at least 10% of the randomized subjects.

- OS using an unstratified Cox model. The hazard ratio associated with treatment will be presented along with the associated two-sided 95% CIs.

A by-subject listing will be presented including treatment arm, OS, whether the subject was censored, and if censored, the reason.

#### **7.5.4.3 Subset Analyses of Overall Survival**

The influence of baseline and demographic characteristics on the treatment effect among randomized subjects will be explored via exploratory subset analyses for the same factors as ORR subset analyses (Section 7.5.1.3).

Number of events and median OS along with 95% CI will be displayed for each treatment group. A forest plot of the OS unstratified hazard ratios (along with 95% CI) will be produced for each level of the subgroups listed above. If subset category has less than 10 subjects per treatment group, HR will not be computed/displayed.

#### **7.5.4.4 Subject Follow-up for Overall Survival**

The minimum follow-up will be reported. The minimum follow-up is defined as the time interval between the last patient's randomization date and the clinical cutoff date.

The extent of follow-up defined as the time between randomization date and last known date alive (for subjects who are alive) or death date (for subjects who died) will be summarized descriptively (median, min, max) for all subjects randomized.

The currentness of follow-up, defined as the time between last OS contact (i.e., last known date alive or death date) and data cut-off date, will be summarized by treatment group. Subjects who died before data cut-off date will automatically have zero value for currentness of follow-up. For subjects with last known date alive after data cut-off date, they will have zero value for currentness of follow-up as well. The currentness of follow-up will be categorized into the following categories: 0 days, 1-3 months, 3-6 months, 6-9 months, 9-12 months and  $\geq 12$  months.

[REDACTED]

#### **7.5.6 Interim Analysis**

One interim analysis will be performed when around 70% of platinum-refractory subjects have been followed for at least 6 months after randomization. The comparison of ORR between nivolumab in combination with ipilimumab vs nivolumab in combination with ipilimumab placebo in platinum refractory randomized subjects will be carried out using a two-sided Cochran-Mantel-Haenszel (CMH) test stratified by the stratification factors as recorded in the IVRS. Using Lan-

DeMets alpha spending function with O'Brien-Fleming boundaries, the significance level for this comparison will be determined by the fraction of subjects included in the interim analysis. If the analysis is performed when exactly 70% of platinum refractory subjects have reached 6 months follow up after randomization, the alpha level is 0.015. Point estimate of ORR, and its corresponding two-sided 98.5% exact CI will be provided for each treatment group. The difference in ORRs between the two treatment groups and its corresponding 98.5% CI will be calculated using CMH methodology and adjusted by the stratification factors as recorded in the IVRS.

The following sensitivity analyses may be conducted using the primary definition of ORR in platinum-refractory subjects:

- If one stratification variable at IVRS and at baseline (CRF and clinical database) disagrees for at least 10% of the randomized subjects, similar analysis of ORR will be performed using the strata as determined at baseline.
- ORR per BICR for subjects with no relevant deviation. This analysis will be conducted only if there are more than 5% subjects with relevant protocol deviations.

The DOR distribution will be estimated using Kaplan-Meier technique. Median survival time along with 95% CI will be provided for each treatment group.

The PFS and OS distribution will also be estimated using Kaplan-Meier technique. Median survival time along with 95% CI will be provided for each treatment group. The hazard ratio and the 95% confidence interval will be estimated in a stratified Cox proportional hazards model using the randomized arm as a single covariate, stratified by PD-L1 status and HPV p-16 status.

Similar descriptive analyses may also be performed for the platinum-eligible subgroups, overall study population (both platinum-eligible and platinum refractory subgroups combined together) and by tumor cellPD-L1, tumor associated immune cell PD-L1, PD-L1 combined positive score (CPS), tumor mutation burden, gene expression profile,, HPV status, and selected other biomarkers status in each subgroup alone or combined.

## **7.6 Safety**

For all safety related analyses, refer to the Core Safety SAP. Safety will be summarized for treated subjects, by arm, as treated. Unless otherwise specified, analyses will be performed for overall and for platinum refractory and platinum eligible subgroups separately.

### **7.6.1 Deaths**

See Core Safety SAP.

### **7.6.2 Serious Adverse Events**

See Core Safety SAP.

### **7.6.3 Adverse Events Leading to Discontinuation of Study Therapy**

See Core Safety SAP.

#### **7.6.4 Adverse Events Leading to Dose Delay of Study Therapy**

See Core Safety SAP.

#### **7.6.5 Adverse Events**

See Core Safety SAP.

#### **7.6.6 Select Adverse Events**

See Core Safety SAP.

#### **7.6.7 Immune Modulating Medication**

See Core Safety SAP.

#### **7.6.8 Multiple Events**

See Core Safety SAP.

#### **7.6.9 Clinical Laboratory Evaluations**

The analysis population for each laboratory test is restricted to treated subjects who underwent that laboratory test.

##### **7.6.9.1 Hematology**

See Core Safety SAP.

##### **7.6.9.2 Serum Chemistry**

See Core Safety SAP.

##### **7.6.10 Immunogenicity**

See Core Safety SAP

##### **7.6.11 Vital Signs and Pulse Oximetry**

See Core Safety SAP.

#### **7.7 Pregnancy**

See Core Safety SAP.

[Redacted]

[Redacted]

[Redacted]

[Redacted]

[Redacted]

[Redacted]

[Redacted]

[Redacted]

[Redacted]

[Redacted]

[Redacted]

[Redacted]

[Redacted]

[Redacted]

## **7.9.2 Analyses**

### **7.9.2.1 Distribution of PD-L1 Expression**

#### Descriptive statistics of PD-L1 expression and PD-L1 status:

- Listing of all PD-L1 IHC data and treatment group, all PD-L1 tested subjects.
- Summary of tumor specimen acquisition and characteristics by treatment group for all randomized subjects.
- Cumulative distribution plot of PD-L1 expression at baseline versus population percentile by treatment group and overall, all evaluable PD-L1 subjects.
- Frequency of PD-L1 expression status by treatment group and overall, all randomized PD-L1 subjects, including indeterminate and not evaluable if over 5% of subjects in the population fall in this category.
- Box plot of PD-L1 expression by treatment group and overall, all randomized subjects

### **7.9.2.2 Association Between PD-L1 Status and Efficacy Measures**

#### **Analyses for ORR per BICR endpoint:**

Evaluation of association between PD-L1+ tumor expression level and ORR in subjects treated with nivolumab/ipilimumab and nivolumab/ipilimumab-placebo

- A separate logistic regression model will be fitted for ORR with PD-L1+ expression level as a sole covariate for subjects treated with nivolumab/ipilimumab vs nivolumab/ipilimumab-placebo, respectively. An appropriate transformation of PD-L1+ expression may be considered depending on an assessment of fit of the model. The following summaries will be presented by treatment arm:
  - Odds ratios corresponding to a 1 and 10% PD-L1 expression change and its associated 95% CI, respectively
  - A plot of estimated response probability with 95% confidence band vs PD-L1+ expression (X-axis)
  - A plot of estimated response probability for each treatment arm in a single plot vs PD-L1+ expression (X-axis)
- Box plot of PD-L1 expression versus Response Status
- Receiver Operating Characteristics (ROC) analysis with ORR will be performed to help assess in-study (re-substitution) predictive accuracy of the logistic regression model and whether there is a clinically meaningful threshold of PD-L1 expression. The following summaries will be provided for treated subjects by treatment arm:
  - A plot of the ROC curve
  - A plot of estimated true positive fraction and false positive fraction vs. PD-L1+ expression (X-axis)

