## 5 SAMPLE SIZE AND POWER

The primary objective is to compare the ORR of nivolumab in combination with ipilimumab vs nivolumab in combination with ipilimumab placebo, as determined by BICR using Response Evaluation Criteria In Solid Tumors (RECIST 1.1) criteria in platinum refractory subjects with recurrent or metastatic SCCHN. The alpha level for the ORR is adjusted for one planned interim analysis using Lan-DeMets alpha spending function with O’Brien-Fleming boundaries, which will be determined by the fraction of subjects included in the interim analysis. Given that the interim analysis for the primary endpoint is expected to be performed when 70% of platinum refractory subjects have reached 6 months follow up after randomization, the alpha level is expected to be 0.015 for the interim analysis and 0.045 for the final analysis.

Approximately 396 subjects (216 platinum refractory subjects and 180 platinum eligible subjects) will be randomized to either nivolumab plus ipilimumab or nivolumab in combination with ipilimumab placebo in a 2:1 ratio.

A sample size of 216 randomized platinum refractory subjects (144 and 72 respectively) will provide 84% power for testing the odds ratio of nivolumab plus ipilimumab over Nivolumab in combination with placebo, with a 0.050 two-sided significance level, assuming ORR of 35% and 15% (odds ratio of 3.051) in the nivolumab plus ipilimumab and nivolumab in combination with ipilimumab placebo treatment group respectively (odds ratio of proportions test using EAST v6).

Only the primary endpoint will be tested, none of the secondary endpoints.

The first secondary objective is to estimate the ORR of the treatment of nivolumab in combination with ipilimumab vs nivolumab in combination with ipilimumab placebo, as determined by BICR using RECIST 1.1 criteria for first line treatment of recurrent or metastatic SCCHN in the platinum eligible setting.

Approximately 180 subjects (120 and 60 respectively) will be randomized in the platinum eligible subgroup. For a sample size of 120 subjects randomized to nivolumab plus ipilimumab, the maximum width of the exact two-sided 95% confidence interval (CI) is 18.6% when the ORR is expected to be in the 10% to 55% range. The table below summarizes the 95% exact CI when observed ORRs are between 10% and 55% respectively.

Table 5-1: Observed ORR with Exact 95% CI in Platinum Eligible Subjects randomized to nivolumab plus ipilimumab (N=120).

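### SAP 7.9.2.2 judges PD-L1 accuracy and looks for a PD-L1 threshold from re-substitution ROC results, with no visible cut-selection rule or optimism correction

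*SAP*

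**What the plan says.** SAP 7.9.2.2 fits, separately in each arm, a logistic model for response with PD-L1 expression as the only covariate, and allows PD-L1 to be transformed after looking at model fit. A ROC analysis follows, to "help assess in-study (re-substitution) predictive accuracy of the logistic regression model and whether there is a clinically meaningful threshold of PD-L1 expression". Its listed summaries, for treated subjects by arm, are the ROC curve and this: "A plot of estimated true positive fraction and false positive fraction vs. PD-L1+ expression (X-axis". The visible text names no rule for picking a threshold, no bootstrap or cross-validation, and no interval for the area under the curve (AUC) or for a threshold.

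Efficacy by PD-L1 expression is a secondary objective in both documents, for the two platinum settings separately and overall (Protocol 1.5.2, SAP 3.2). SAP 7.9.2.3 then models the treatment by PD-L1 interaction with a cut-off written only as X%.

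**The concern.** The section sets itself two questions: how well PD-L1 predicts response, and whether a useful threshold exists. It answers both from the data that fitted the model. Scanning the curves for the most promising PD-L1 value picks a maximum over noisy estimates, and that maximum is positive on average even when PD-L1 carries no information. The fewer the responders, the larger the spurious separation.

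At stake is the reading of a secondary objective: an apparent threshold, or apparent discrimination, that would not recur in new patients. Since the control arm is smaller and has the lower assumed response rate, it is the arm more likely to show one by chance.

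**Working it through.** **Inputs.** SAP 5: "A sample size of 216 randomized platinum refractory subjects (144 and 72 respectively" in the combination and control arms, "assuming ORR of 35% and 15% (odds ratio of 3.051". SAP 5 also: "Approximately 180 subjects (120 and 60 respectively) will be randomized in the platinum eligible subgroup". SAP 2.2: up to 20% of randomized subjects may have a non-evaluable or indeterminate PD-L1 result. Not in the documents, so assumed: the PD-L1 distribution (40% at zero, skewed above), 13 candidate cuts from 1% to 90%, and a 15% response rate among platinum eligible controls.

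**1. The plan's own figure.** The SAP gives no figure for the ROC analysis. The power statement fixes the sample sizes and rates used here: "will provide 84% power for testing the odds ratio", two-sided 0.050. With a Wald test of the log odds ratio:

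- ln(3.051) = 1.115
- SE = sqrt(1/(144 × 0.35 × 0.65) + 1/(72 × 0.15 × 0.85)) = 0.373
- power = Φ(1.115/0.373 − 1.960) = 84.8%

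This agrees with the stated 84% to within one point.

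**2. Expected responders.**

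- Refractory combination: 144 × 0.35 = 50.4
- Refractory control: 72 × 0.15 = 10.8; if 20% lack a PD-L1 value, 0.8 × 10.8 = 8.6
- Whole control arm: 72 + 60 = 132; 132 × 0.15 = 19.8

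**3. What is and is not biased.** Let J(c) be the true positive fraction minus the false positive fraction at cut c (the Youden index). With no association, J(c) averages 0 at any fixed c; simulation at the 1% cut gave about 0.00 in both arms. With one covariate, a monotone transformation leaves the ranks, and hence the ROC, unchanged. The bias lies in the maximum of J(c) over c and in letting the fitted slope set the direction.

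The noise being maximised can be gauged at a cut that half the subjects exceed, where SE(J) = sqrt(0.25/responders + 0.25/non-responders):

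- 50 and 94: sqrt(0.00500 + 0.00266) = 0.088
- 11 and 61: sqrt(0.02273 + 0.00410) = 0.164
- 20 and 112: sqrt(0.01250 + 0.00223) = 0.121

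The refractory control arm has nearly twice the noise of the refractory combination arm.

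**4. Simulation with no association (true J = 0).** High PD-L1 was taken as favourable. The correction used 100 bootstrap resamples, repeating the cut search in each.

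| Group | Subjects / responders | Mean best J | 90th percentile | Mean after correction |
|---|---|---|---|---|
| Refractory combination | 144 / 50 | 0.07 | 0.16 | 0.02 |
| Refractory control | 72 / 11 | 0.14 | about 0.30 | 0.06 |
| Whole control arm | 132 / 20 | 0.10 | not tabulated | not tabulated |

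A repeat run gave 0.05 for the corrected refractory control value, so its second decimal is not firm.

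With the direction taken from the fitted slope, the AUC (truly 0.50) averages 0.54 in the refractory combination arm and 0.56 in the refractory control arm. Correction brings these to 0.51 and 0.52.

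**5. Sensitivity to the search.** If every observed PD-L1 value is a candidate cut and the data also set the direction, the median best J rises to 0.13–0.14 (refractory combination), 0.23–0.25 (refractory control) and 0.18–0.19 (whole control arm). With 58 refractory controls and 9 responders it is 0.25–0.27. The ranges cover a continuous marker and one with 40% at zero. That the answer depends this much on the rule is itself a reason to state one.

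**The case against.** The best case for the plan is that nothing it lists as output is biased. It plots fractions over the whole PD-L1 range, reports no best cut, and calls the accuracy re-substitution, so readers are told what they are looking at. SAP 5 tests only the primary endpoint, SAP 7.5 limits p-values to that comparison, and SAP 7.9.2.3 says the study is not powered for the interaction. No decision depends on the ROC.

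Much of this stands, and it rules out several stronger readings that a reader might infer:

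- **That the plotted fractions are themselves inflated.** At a fixed PD-L1 value they are not.
- **That choosing a transformation on fit adds ROC optimism.** A monotone one cannot, and no other kind is mentioned.
- **That the plan compares ROC accuracy between arms on unequal terms.** It plans separate plots and no contrast.
- **That the ROC threshold will become the X% of SAP 7.9.2.3.** The visible text never says so. Stratification and SAP 7.9.2.4 use a pre-specified 1% cut, and the PD-L1 definitions (SAP 4.3.6) and the opening of 7.9 are redacted, so the cut-offs or a caveat may be there.
- **That 11 responders is the planned denominator.** The ROC text names no platinum subgroup. The refractory-only reading is inferred from SAP 3.2 and from the general rule in SAP 7.5, a different section.

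What does not stand is that the label settles the matter. The SAP says the ROC will help assess whether a threshold exists. Answering that means looking for a promising cut, and naming the method as re-substitution does not remove the optimism from the answer.

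**Conclusion.** The point holds as a minor improvement to exploratory work. Accuracy and the existence of a PD-L1 threshold are to be judged on uncorrected same-sample results, with no stated rule for choosing the cut. If a best cut is read off, a marker with no association shows a mean Youden index of about 0.07 in the refractory combination arm, 0.14 in the refractory control arm and 0.10 in the whole control arm.

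These sizes rest on the assumed PD-L1 distribution, the 13 candidate cuts, the design response rates and, for the whole control arm, 15% throughout. A freer search gives larger values. The primary comparison and its alpha are unaffected. A correction in redacted text cannot be excluded.

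**What to change.** Add to SAP 7.9.2.2:

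- One cut-selection rule, for example the maximum Youden index over a listed set of PD-L1 values.
- By arm, bootstrap optimism-corrected AUC, and corrected true and false positive fractions at the selected cut, shown beside the apparent values. The cut search, and the direction if the data set it, is repeated in each resample.
- A statement that any threshold found is hypothesis-generating and is not used as the cut-off in this trial's own PD-L1 subgroup or interaction analyses.

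If the redacted text already fixes the cut-offs, a cross-reference would serve for the last item.

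The cost is a short bootstrap routine, a few sentences of SAP text and slightly less favourable reported accuracy. No data collection, sample size or confirmatory analysis changes. The correction reduces the bias but does not remove it: about 0.06 remains in the refractory control arm, so the number of responders should be shown with the corrected values.

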#### **Analyses for PFS per BICR endpoint:**

- A separate Cox proportional hazards regression model will be fitted for PFS with PD-L1+ expression level as a sole covariate among all subjects treated with nivolumab/ipilimumab and nivolumab/ipilimumab-placebo, respectively. An appropriate transformation of PD-L1+ expression may be considered depending on an assessment of fit of the model. The following summaries will be presented by treatment arm:
  - The hazard ratios corresponding to 1 and 10% PD-L1+ expression change along with its associated 95% CI, respectively
  - A plot of estimated  $\log_e(\text{hazard})$  with 95% confidence band vs PD-L1+ expression(X-axis)
  - A plot of estimated  $\log_e(\text{hazard})$  for each treatment arm in a single plot vs. PD-L1+ expression(X-axis)
- For each of the PD-L1 expression status subgroup:
  - PFS curves will be estimated using the Kaplan-Meier product limit method for each treatment group. Two-sided, 95% confidence intervals for median PFS will be computed by Brookmeyer and Crowley method.
  - Forest plot of Hazard Ratios with 95% CIs.

#### **Analyses for OS endpoint:**

- A separate Cox proportional hazards regression model will be fitted for OS with PD-L1+ expression level and among subjects treated with nivolumab/ipilimumab and nivolumab/ipilimumab-placebo, respectively. An appropriate transformation of PD-L1+ expression may be considered depending on an assessment of fit of the model. The following summaries will be presented by treatment arm:
  - Hazard ratios corresponding to a 1 and 10% PD-L1+ expression change and its associated 95% CI, respectively
  - A plot of estimated  $\log_e(\text{hazard})$  with 95% confidence band vs PD-L1+ expression(X-axis)
  - A plot of estimated  $\log_e(\text{hazard})$  for each treatment arm in a single plot vs. PD-L1+ expression(X-axis)
- For each of the PD-L1 expression status subgroup:
  - OS curves will be estimated using the Kaplan-Meier product limit method for each treatment group. Two-sided, 95% confidence intervals for median OS will be computed by Brookmeyer and Crowley method.
  - Forest plot of Hazard Ratios with 95% CIs.

